9.4 Unscheduled Visit/Telephone Contact

Subjects will be contacted by phone on Days 8, 22 and 36 to assess tolerability and the occurrence of any early treatment-emergent adverse events and to reinforce compliance.

At any time during the study, the subject may have an additional study visit/phone call if the investigator or the subject feels it is necessary. All information, including reason for visit/phone call, AEs, and any procedures performed should be collected in the source documents and recorded in the appropriate section of the eCRF.

9.5 Clinical Laboratory & Pharmacokinetic Evaluations

Clinical laboratory evaluations will be performed at Visits 1, 3, 6, 9, 10, 12, 14, 16, and 17 and every 6 months afterwards or at any time during the study as deemed necessary by the investigator to assess potential health issues or AEs. Samples will be collected at Visits 1, 3, 9, 10, 14, 16 and 17 and every 12 months afterwards for urinalysis. Female subjects (of childbearing potential) will undergo a serum β -hCG pregnancy test at Visits 1 and 10 and a urine β -hCG pregnancy test at Visits 3 and 9 or at any time pregnancy is suspected. Additionally, blood samples will be drawn to determine plasma levels of concomitant AED (OXC, TPM, CBZ, VPA, LTG, LMD and LEV only) prior to study drug administration (Visit 3) and during steady-state concomitant treatment with YKP3089 (Visits 7 and 8). At Visits 7 and 8, additional blood samples (~8 mL each) will be collected for the determination of YKP3089 plasma levels: the first one will be collected upon subjects' arrival to the study unit; the second one should be collected within 2 to 4 hours after the first blood draw. Additional blood samples may be drawn for levels of concomitant AEDs during the double-blind treatment phase if the investigator

believes that symptoms of toxicity may be related to concomitant AEDs, rather than the study drug, and during the open-label extension phase for any reason; these samples will be analyzed by the local laboratory. Time and date of each blood draw and dosing records (time/date/dose) of YKP3089 and AEDs prior to each blood draw will be recorded on the CRF.

All safety laboratory samples will be analyzed by a central laboratory. Plasma samples will be assayed for YKP3089 and AEDs at a specified bioanalytical laboratory using previously validated methods. Assay methodology will be detailed in separate assay protocols.

10 SAFETY AND ADVERSE EVENTS

10.1 Definitions

10.1.1 *Adverse Events*

An adverse event (AE) is any symptom, sign, illness, or experience that develops or worsens in severity during the course of the study. Intercurrent illnesses or injuries should be regarded as AEs. Abnormal results of diagnostic procedures are considered to be AEs if the abnormality:

- Results in study withdrawal
- Is associated with an SAE
- Is associated with clinical signs or symptoms
- Leads to additional treatment or to further diagnostic tests
- Is considered by the investigator to be of clinical significance

10.1.2 *Serious Adverse Event*

AEs are classified as serious or non-serious. A *serious adverse event* is any AE that is:

- Fatal
- Life-threatening
- Requires or prolongs hospital stay
- Results in persistent or significant disability or incapacity
- A congenital anomaly or birth defect

- An important medical event

Important medical events are those that may not be immediately life threatening but are clearly of major clinical significance. They may jeopardize the subject and may require intervention to prevent one of the other serious outcomes noted above. For example, drug overdose or abuse, a seizure that did not result in inpatient hospitalization, or intensive treatment of bronchospasm in an emergency department would typically be considered serious.

10.1.3 *Suspected Adverse Reaction*

Suspected adverse reaction means any AEs for which there is a reasonable possibility that the drug cause the AE. For the purpose of investigational new drug (IND) safety reporting, “reasonable possibility” means there is evidence to suggest a causal relationship between the drug and AE. Suspected adverse reaction implies a lesser degree of certainty about causality than adverse reaction, which means any AE caused by a drug.

All AEs that do not meet any of the criteria for seriousness should be regarded as *non-serious AEs*.

10.1.4 *Adverse Event Reporting Period*

The study period during which AEs must be reported is normally defined as the period from the initiation of any study procedures to the end of the study treatment follow-up, which for this study is 21 days. For this study, the AE reporting period is defined as 30 days following the last administration of study treatment.

10.1.5 *Preexisting Condition*

A preexisting condition is one that is present at the start of the study. A preexisting condition should be recorded as an AE if the frequency, intensity, or the character of the condition worsens during the study period.

10.2 General Physical Examination Findings

At Screening and prior to Visit 3, any clinically significant abnormality should be recorded as a preexisting condition. At the end of the study, any new clinically significant findings/abnormalities that meet the definition of an AE must also be recorded and documented as an AE.

Post-study Adverse Events

All unresolved AEs should be followed by the investigator until the events are resolved, the subject is lost to follow-up, or the AE is otherwise explained. At the last scheduled visit, the investigator should instruct each subject to report any subsequent event(s) that the subject, or the subject's personal physician, believes might reasonably be related to participation in this study.

The investigator should notify the study Sponsor of any death or AE occurring at any time after a subject has discontinued or terminated study participation that may reasonably be related to this study. The Sponsor should also be notified if the investigator should become aware of the development of cancer or of a congenital anomaly in a subsequently conceived offspring of a subject who has participated in this study.

Abnormal Laboratory Values

A clinical laboratory abnormality should be documented as an AE if *any one of the following* conditions is met:

- The laboratory abnormality is not otherwise refuted by a repeat test to confirm the abnormality.
- The abnormality suggests a disease and/or organ toxicity.
- The abnormality is of a degree that requires active management (eg, change of dose, discontinuation of the drug, more frequent follow-up assessments, further diagnostic investigation).

Hospitalization, Prolonged Hospitalization, or Surgery

Any AE that results in hospitalization or prolonged hospitalization should be documented and reported as a serious AE unless specifically instructed otherwise in this protocol. Any condition responsible for surgery should be documented as an AE if the condition meets the criteria for an AE.

Neither the condition, hospitalization, prolonged hospitalization, nor surgery are reported as an AE in the following circumstances:

- Hospitalization or prolonged hospitalization for diagnostic or elective surgical procedures for a preexisting condition. Surgery should **not** be reported as an outcome of an AE if the purpose of the surgery was elective or diagnostic and the outcome was uneventful.
- Hospitalization or prolonged hospitalization required to allow efficacy measurement for the study.
- Hospitalization or prolonged hospitalization for therapy of the target disease of the study, unless it is a worsening or increase in frequency of hospital admissions as judged by the clinical investigator.
- An Emergency Room visit is not considered hospitalization.

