12.8 Safety Variable Analyses

All ITT subjects will be evaluable for safety. The number and percent of subjects reporting AEs (including treatment-emergent laboratory abnormalities) will be tabulated by randomized treatment group. All serious AEs (SAEs) will be tabulated separately as well as included with all reported AEs.

Physical and neurologic assessments, laboratory results, vital signs (including orthostatic measurements), ECGs, and C-SSRS will be summarized using descriptive statistics.

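### Protocol 10.2 makes an unrefuted laboratory abnormality an adverse event with no significance threshold while 10.1.1 sets one, so laboratory AE counts depend on which rule a site follows

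*Protocol*

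**What the plan says.** Two sections of the protocol say when an abnormal test result becomes an adverse event.

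- **10.1.1** gives the general rule: "Abnormal results of diagnostic procedures are considered to be AEs if the abnormality" meets one of five criteria. In short, these are study withdrawal, association with an SAE, association with signs or symptoms, a consequence ("Leads to additional treatment or to further diagnostic tests"), or judgement ("Is considered by the investigator to be of clinical significance").
- **10.2, Abnormal Laboratory Values**, gives the laboratory rule. An abnormality should be documented as an AE if "any one of the following" conditions holds. The first is "The laboratory abnormality is not otherwise refuted by a repeat test to confirm the abnormality". The second is "The abnormality suggests a disease and/or organ toxicity". The third is that its degree calls for active management.

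For examination findings at the end of the study, the opening of 10.2 asks for both tests together: "any new clinically significant findings/abnormalities that meet the definition of an AE must also be recorded".

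Section 12.8 carries the result into the analysis: the number and percent of subjects "reporting AEs (including treatment-emergent laboratory abnormalities) will be tabulated by randomized treatment group". Section 13.7.2 makes adverse events the primary data for the DMC and also gives it access to all other safety data.

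**The concern.** Because the 10.2 conditions are joined by OR, the first is sufficient alone. It asks nothing about degree, clinical meaning or consequence. It is met by any abnormality that was confirmed, and on a literal reading by any that nobody repeated. It reads like a confirmation step that was placed in a list of alternatives.

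The synopsis plans about 100 sites, each holding a protocol with two rules. If some follow 10.1.1 and others 10.2, the same value is an AE at one site and not at another. What is at stake is consistent ascertainment of laboratory AEs, and the meaning of the overall AE rates and laboratory-term rows in the 12.8 tables and the DMC reviews.

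**Working it through.** **Step 1: set the rules side by side.** Take a value that develops on treatment, with no symptoms, SAE, treatment or withdrawal, and judged not clinically significant unless stated.

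| Case | 10.2 | 10.1.1 |
|---|---|---|
| Never repeated | AE (first bullet) | Not an AE |
| Repeated and confirmed | AE (first bullet) | Not an AE, unless the repeat counts as a further diagnostic test |
| Repeated and normal | Not an AE | Not an AE, unless the repeat counts as a further diagnostic test |
| Normal on repeat, but suggested organ toxicity or led to withdrawal | AE (second or third bullet) | AE if it led to withdrawal or was judged significant |

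The first row conflicts outright. The next two depend on how a repeat test is classified: if it counts, a value that normalises is an AE under 10.1.1 but fails the first 10.2 bullet. The last row shows that the second and third bullets still do work of their own.

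**Step 2: can the size be derived?** The documents state no abnormality rate, so there is no figure to reproduce. The following is illustration on assumed inputs.

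- *k*, analytes: 6.3 lists about 27, assuming a five-part differential and three red-cell indices (13 haematology + 14 chemistry). Correlation would lower the effective number; 5 to 27 is used.
- *v*, post-dose double-blind draws: 2 (Visits 6 and 9), or 3 with Visit 10 for subjects not entering the extension (9.5).
- *q*, chance that one value is abnormal and unrefuted: assumed. A 95% reference range with no repeats gives 5%. If every flagged value were repeated independently, 0.05 × 0.05 = 0.25%.

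Share of subjects with at least one such value, under independence: 1 − (1 − q)^(kv).

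| q | k | Draws | Result |
|---|---|---|---|
| 0.25% | 10 | 1 | 1 − 0.9975^10 = 2.5% |
| 0.25% | 27 | 1 | 1 − 0.9975^27 = 6.5% |
| 5% | 10 | 1 | 1 − 0.95^10 = 40% |
| 5% | 27 | 1 | 1 − 0.95^27 = 75% |
| 0.5% | 10 | 2 | 1 − 0.995^20 = 9.5% |
| 2.5% | 19 | 2 | 1 − 0.975^38 = 62% |
| 5% | 27 | 3 | 1 − 0.95^81 = 98% |

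If values are perfectly correlated across visits, the exponent is k alone: q = 0.5%, k = 5 gives 1 − 0.995^5 = 2.5%, and q = 5%, k = 19 gives 1 − 0.95^19 = 62%.

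**Step 3: which rows would be affected?** Assume a true event of 2% versus 10%, 100 per arm, two-sided 0.05, normal approximation for two proportions. An unrelated background *b* on the same row changes the rates to 1 − 0.98(1 − b) and 1 − 0.90(1 − b).

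| b per arm | Rates on the row | Power |
|---|---|---|
| 0 | 2.0% v 10.0% | 67% |
| 2.5% | 4.5% v 12.3% | 51% |
| 5% | 6.9% v 14.5% | 41% |
| 10% | 11.8% v 19.0% | 29% |
| 25% | 26.5% v 32.5% | 15% |
| 50% | 51.0% v 55.0% | 8% |
| 75% | 75.5% v 77.5% | 5% |

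The large backgrounds belong to a pooled any-AE row, the small ones to a single laboratory term. A preferred-term row for a different event has b = 0 and is unaffected.

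**The case against.** A reader might infer that routine out-of-range values would swamp the AE tables and mask real signals, or that 40% to 75% of subjects would have a 10.2 event at each draw. The documents do not support either statement. They give no abnormality rate and do not define a laboratory abnormality as any out-of-range value. The 40% to 75% ignores refutation on repeat and values already abnormal before dosing, although the AE definition requires something that develops or worsens and 12.8 refers to treatment-emergent abnormalities.

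On masking, the extension tables are by system organ class and preferred term (SAP 11.3.1), so an unrelated laboratory term does not dilute another row. What remains is narrower: the possible DRESS case in protocol 4.6 included eosinophilia and hepatic enzyme abnormalities, and marginal values of those analytes could fall on the same laboratory-term rows.

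There is real mitigation. The double-blind period has a concurrent placebo group, and blinding gives no reason for site habits to differ by arm, so the effect is noise rather than bias. Laboratory results are also summarised separately (12.8; shift tables in SAP 11.3.2), and the DMC can see them. The double-blind SAP and the data entry manual are not among the documents, so either may add guidance. None of this makes the AE counts themselves consistent.

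It can also be argued that 10.1.1 and 10.2 are additive and that broad capture is a defensible choice for this drug. Read that way, the 10.1.1 criteria would have almost no role for laboratory results, and the protocol does not say that this is intended.

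**Conclusion.** The point holds as an inconsistency that should be reconciled. The first 10.2 bullet makes an unrefuted laboratory abnormality an AE with no significance threshold, and 10.1.1 does not. AE status then turns on the rule chosen and on whether the test was repeated, and the counts in 12.8 and the DMC reviews inherit that.

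The likely effect is non-specific noise in all arms, on overall AE rates and laboratory-term rows. Its size is unknown: from about 2.5% to 98% of subjects on the assumed inputs, which is too wide to support any claim beyond the possibility of inflation. The textual finding rests on the literal OR wording of 10.2 and on 10.1.1 being meant as a criterion for laboratory results; it does not depend on the assumed rates.

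**What to change.** Reconcile the two sections by removing the first 10.2 bullet as a standalone trigger. The rule could read: a laboratory abnormality is documented as an AE if it suggests disease or organ toxicity, requires active management, or meets any criterion in 10.1.1; a repeat done only to confirm a value does not by itself count as a further diagnostic test.

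Non-refutation should not become a precondition for every route. An abnormality that met one of these criteria and later normalised must remain an AE, and a blanket precondition could drop it.

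Keep all out-of-range values in the laboratory summaries and listings. The cost is about a sentence in the protocol and a line in the eCRF completion guidance. The downside is small: fewer isolated, insignificant values appear in the AE tables, but they stay in the central laboratory data.

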10.3 Adverse Event Recording and Assessing

All AEs occurring during this clinical trial will be recorded. The investigator will review each event and assess its relationship to drug treatment (unrelated, remote, possible, probable, or definite). Each sign or symptom reported will be graded on a 3-point severity scale (mild, moderate, or severe), and the date of onset, time of onset, and outcome of each event will be noted.

The relationship of each AE to study drug will be assessed using the following definitions:

Definite	
• Distinct temporal relationship with drug treatment• Known reaction to agent or chemical group, or predicted by known pharmacology
----------	--

	
 • Event cannot be explained by subject’s clinical state or other factors
Probable	
 • Reasonable temporal relationship with drug treatment • Likely to be known reaction to agent or chemical group, or predicted by known pharmacology • Event cannot easily be explained by subject’s clinical state or other factors
Possible	
 • Reasonable temporal relationship with drug treatment • Event could be explained by subject’s clinical state or other factors
Remote	
 • Poor temporal relationship with drug treatment • Event easily explained by subject’s clinical state or other factors
Unrelated	
 • Event occurring before dosing • Event or intercurrent illness due wholly to factors other than drug treatment

The following definitions for rating severity will be used:

- *Mild*: The AE is easily tolerated and does not interfere with daily activity.
- *Moderate*: The AE interferes with daily activity, but the subject is still able to function.
- *Severe*: The AE is incapacitating and requires medical intervention.

10.4 Reporting of Adverse Events

At each contact with the subject, the investigator must seek information on AEs by specific questioning and, as appropriate, by examination. Information on all AEs should be recorded immediately in the source document and also in the appropriate AE module of the CRF. All clearly related signs, symptoms, and abnormal diagnostic procedures results should recorded in the source document, though they should be grouped under one diagnosis.

All AEs occurring during the study period must be recorded on the appropriate eCRFs. The clinical course of each event should be followed until resolution, stabilization, or until it has been determined that the study treatment or participation is not the cause. Serious AEs that are still ongoing at the end of the study period must be followed up to determine the final outcome. Any

serious AE that occurs after the study period and is considered to be possibly related to the study treatment or study participation should be recorded and reported immediately.

10.4.1 ***Study Sponsor Notification by Investigator***

In the event of any fatal or life-threatening SAE, the investigator must inform SK Life Science, Inc. (SKLSI) designee PPD by telephone immediately. Any non-fatal or non-life-threatening SAE, regardless of expectedness or causality, must be reported on the SAE Report Form by fax to SKLSI’s designee PPD within one business day of the investigator’s or any other study center personnel’s knowledge of the event as described below.

A completed SAE Report Form, the AE record, pertinent medical records, and the Concurrent Medication record from the source documents should be faxed to SKLSI’s designee PPD within one business day of the investigator’s or any study center personnel’s knowledge of a serious event. An updated SAE Report Form should be forwarded to SKLSI’s designee PPD within one business day of receipt of new/updated information. The SAE Reporting Requirements and contact information are outlined in [Table 7](#).

Seizures in this refractory subject population are anticipated with the weekly seizure frequency used as a primary study endpoint. Therefore, seizures, in and of themselves, will not be considered adverse events. Seizures to be considered adverse events will include those occurring with a measurable increase over the subject’s typical seizure frequency or duration; or multiple seizures in a pattern distinguishable from the usual seizure pattern.

*** The SAE report form must be used for reporting.**

At the time of the initial report, the investigator should provide as much of the following information as possible:

- Study identifier
- Study center
- Subject number
- A description of the event
- Date of onset
- Current status
- Whether study treatment was discontinued
- The reason why the event is classified as serious
- Investigator assessment of the association between the event and study treatment

Within the following 48 hours, the investigator must provide further information on the serious AE in the form of a written narrative. This should include a copy of the completed SAE form, and any other diagnostic information that will assist the understanding of the event. Significant new information on ongoing serious AEs should be provided promptly to the study Sponsor.

10.4.2 Ethics Committee/Institutional Review Board Notification by Investigator

Reports of all serious AEs (including follow-up information) must promptly be submitted to the Ethics Committee/Institutional Review Board (EC/IRB). Copies of each report and documentation of EC/IRB notification and receipt will be kept in the clinical investigator's binder.

10.4.3 *Regulatory Authority Notification of IND Safety Reports by Sponsor*

The study Sponsor must notify the FDA and all participating investigators in an IND safety report of potential serious risks from clinical trials as soon as possible but in no case later than 15 calendar days after the Sponsor determines that the information qualifies for reporting. This includes any suspected adverse reaction that is both serious and unexpected (SUSAR).

The study Sponsor must notify the FDA of any unexpected fatal or life-threatening suspected adverse reaction as soon as possible but no later than 7 calendar days from the Sponsor's initial receipt of the information.

If a previous AE that was not initially deemed reportable is later found to fit the criteria for reporting, the study Sponsor will submit the AE in a written report to the FDA as soon as possible, but no later than 15 calendar days from the time the determination is made.

The notification of other Regulatory Authorities follows the same procedure and timeframe, per ICH Guidance, as for the FDA.

10.5 Withdrawal of Subject from Study

Subjects may be withdrawn from the study prior to completion of the study if:

- Consent is withdrawn by the subject
- The subject fails to adhere to the protocol requirements
- An intolerable AE is experienced
- The subject becomes pregnant
- The subject is lost to follow-up

When a subject is withdrawn, the discharge procedures must be performed. The reason(s) for the withdrawal must be documented in the subject's eCRF.

11 DATA HANDLING PROCEDURES

11.1 Data Handling and Record Keeping

11.1.1 *Confidentiality*

Information about study subjects will be kept confidential and managed according to the requirements of the Health Insurance Portability and Accountability Act (HIPAA). Those regulations require a signed subject authorization informing the subject of the following:

- What protected health information (PHI) will be collected from subjects in this study
- Who will have access to that information and why
- Who will use or disclose that information
- The rights of a research subject to revoke their authorization for use of their PHI

The subjects will be told that representatives of the Sponsor, IRB/IEC, or regulatory authorities may inspect their medical records to verify the information collected and that all personal information made available for inspection will be handled in strictest confidence and in accordance with local data protection laws.

In the event that a subject revokes authorization to collect or use PHI, the investigator, by regulation, retains the ability to use all information collected prior to the revocation of subject authorization. For subjects who have revoked authorization to collect or use PHI, attempts should be made to obtain permission to collect at least vital status (ie, that the subject is alive) at the end of his or her scheduled study period.

11.1.2 *Source Documents*

Source data is all information, original records of clinical findings, observations, or other activities in a clinical trial necessary for the reconstruction and evaluation of the trial. Source data are contained in source documents. Examples of these original documents and data records include hospital records; clinical and office charts; laboratory notes; memoranda; subjects' diaries or evaluation checklists; pharmacy dispensing records; recorded data from automated instruments; copies or transcriptions certified after verification as being accurate and complete;

microfiches; photographic negatives; microfilm or magnetic media; x-rays; subject files; and records kept at the pharmacy, at the laboratories, and at medico-technical departments involved in the clinical trial.

11.1.3 *Electronic Case Report Forms*

The eCRF is the primary data collection instrument for the study. All data requested on the eCRF must be recorded. All missing data must be explained. Details of the completion of the eCRF will be included in a data entry manual.

11.1.4 *Records Retention*

In compliance with the ICH/GCP guidelines, the investigator/institution will maintain all eCRFs and all source documents that support the data collected from each subject, as well as all study documents as specified in ICH/GCP Section 8, Essential Documents for the Conduct of a Clinical Trial, and all study documents as specified by the applicable regulatory requirement(s).

The investigator/institution will take measures to prevent accidental or premature destruction of these documents. Essential documents must be retained until at least 2 years after the last approval of a marketing application in an ICH region and until there are no pending or contemplated marketing applications in an ICH region or until at least 2 years have elapsed since the formal discontinuation of clinical development of the investigational product. These documents will be retained for a longer period if required by the applicable regulatory requirements or by an agreement with the Sponsor. It is the responsibility of the Sponsor to inform the investigator/institution as to when these documents no longer need to be retained.

If the responsible investigator retires, relocates, or for other reasons withdraws from the responsibility of keeping the study records, custody must be transferred to a person who will accept the responsibility. The Sponsor must be notified in writing of the name and address of the new custodian. Under no circumstance shall the investigator relocate or dispose of any study documents before having obtained written approval from the Sponsor. If it becomes necessary for the Sponsor or the appropriate regulatory authority to review any documentation relating to this study, the investigator must permit access to such reports.

The following records are considered essential documents:

- Signed informed consent documents for all subjects
- Subject identification code list, Screening log (if applicable), and enrollment log
- Record of all communications between the investigator and the IRB/IEC
- Composition of the IRB/IEC or other applicable statement
- Record of all communications between the investigator and Sponsor (or CRO)
- List of sub-investigators and other appropriately qualified persons to whom the investigator has delegated significant trial-related duties, together with their roles in the study and their signatures
- Compact Disks (CDs) of eCRFs and related documentation of corrections for all subjects
- Drug accountability records
- Record of any body fluids or tissue samples retained
- All other source documents (subject records, hospital records, laboratory records, etc)
- All other documents as listed in *Section 8* of the ICH consolidated guideline on GCP (Essential Documents for the Conduct of a Clinical Trial) and any applicable country requirements.

